## Background and aim

The new coronavirus 2019 (COVID-19) was declared a pandemic by the World Health Organization (WHO) due to the alarming levels of spread, severity and inaction. COVID-19 is caused by the SARS-CoV-2 virus (severe acute respiratory syndrome of coronavirus 2). The main clinical characteristics observed in patients infected with COVID-19 are: fever, dry cough, fatigue or myalgia. Patients infected with COVID-19 can present from no symptoms to pneumonia and death. Dealing with COVID-19 must be done on different fronts, such as mitigation, treatment and prevention. Therefore, strategies and therapies that can help reduce the COVID-19 rate of contamination are still important alternatives at this time of the pandemic, especially when mutations of the virus have been observed worldwide.

The Advanced Penetration Technology™ (APT™) is intellectual property owned by Patient Focused Tele-Health, LLC, a Rockwall, Texas based company. The company's focus is improving over-the-counter (OTC) topical formulations, allowing consumers better therapeutic outcomes with non-prescription medications. The Advanced Penetration Technology™ (APT™) is a patent-pending, proprietary transdermal dual carrier formulation. This formulation provides improved dermal penetration and efficacy of topical API's. Additionally, the APT™ imparts both a mechanical and biochemical effect on the microbe/fungal cell walls providing a highly effective method of destruction of microbes. These unique properties impart the broad spectrum anti-viral capability to the APT™ Tetracycline 3% formulation, breaking barriers in pharmacology and virology.

The topical formulation APT™ Tetracycline 3% formulation (APT™ T3X), is a FDA registered, non-prescription product. This formulation is used in an off-label manner as an intranasal application for prevention of COVID-19 and other viruses. The APT™ T3X as a topical application will penetrate through and into the mucus layer and deeper. This barrier of coverage will provide a mitigation effect to decrease the viral load of exposure and infection. The efficacy of APT™ T3X is due to disrupting the lipid envelope in seconds, hence neutralizing the virus. Previous tests were performed with APT™ T3X and the results found were promising. However, these tests were performed only *in vitro* and clinical studies demonstrating the ability of the APT™ T3X to decrease viral exposure and contamination by COVID-19 are necessary to confirm the possible prophylactic effect, allowing the formulation to be widely distributed to the general population.

Therefore, the aim of this project will be to evaluate the efficacy of the APT™ T3X compared to placebo to decrease COVID-19 contamination rate in humans.

# Methods

## *Trial design*

A two-arm, parallel randomized, triple-blinded (volunteers, care provider, and outcome assessor), placebo-controlled trial will be carried out. This trial it will be prospectively registered on clinicaltrials.gov.

## *Ethics*

This study was submitted and approved by the Research Ethics Committee of Irmandade da Santa Casa de Misericórdia de Porto Alegre – ISCMIA, Porto Alegre, Rio Grande do Sul, Brazil, under protocol number 4.485.847. This trial will be performed in accordance with the Declaration of Helsinki and the guidelines for research involving human subjects. All volunteers will sign the written informed consent before enrolment in the study.

## *Volunteers and recruitment*

One hundred volunteers will be included in the trial (fifty volunteers per group). The inclusion criteria will be: over 18 years; good general health (without serious health problems); tested negative, by means of immunoglobulin (Ig) G and IgM serology tests and chain real-time polymerase chain reaction (RT-PCR), for COVID-19. The exclusion criteria will be: previous immunization against COVID-19; allergy to tetracycline hydrochloride; diagnosis of Lyme disease; immunocompromised; share housing with someone diagnosed with COVID-19 at the time of the baseline evaluation; serious illnesses, such as cancer, kidney failure, decompensated cardiorespiratory and metabolic diseases, etc.

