### *Interventions*

Volunteers will be instructed to use the intervention, according to the prior randomization, once a day, every day, for 21 days. If the volunteer is health professional, it will be instructed to use the intervention twice a day, every day, for 21 days. Intervention specifications included:

- 1) APT™ T3X: The volunteers will be instructed to use 4 drops of tetracycline hydrochloride 3% (APT™ T3X) applied inside of the nasal channels and inside of nostrils.
- 2) Placebo: The volunteers will be instructed to use 4 drops of a formulation composed of FDA approved inactive ingredients applied inside of the nasal channels and inside of nostrils.

All volunteers will be instructed to record each intervention application and to send to a member of the research team in order to control and ensure the adherence to treatment.

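### Cheap safety improvement: no eligibility criterion concerns the nose, so volunteers with damaged nasal lining may be given a penetration-enhancing product intranasally for 21 days

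*Combined protocol and SAP*

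**What the plan says.** The section Volunteers and recruitment contains all the eligibility criteria. Volunteers must be over 18, in "good general health (without serious health problems", and negative for COVID-19 on serology and RT-PCR. The exclusions begin with "previous immunization against COVID-19; allergy to tetracycline hydrochloride; diagnosis of Lyme disease; immunocompromised". They continue with sharing a home with someone diagnosed with COVID-19 at the baseline evaluation, and end with "serious illnesses, such as cancer, kidney failure, decompensated cardiorespiratory and metabolic diseases, etc". The planned size is given in the same section: "One hundred volunteers will be included in the trial (fifty volunteers per group".

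The section Interventions places four drops, active or placebo, "applied inside of the nasal channels and inside of nostrils". The schedule is "once a day, every day, for 21 days", or twice a day for health professionals.

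Background and aim describes the active product as a transdermal dual-carrier formulation: "This formulation provides improved dermal penetration and efficacy of topical API's". As a topical application it "will penetrate through and into the mucus layer and deeper". The same section calls the formulation an FDA-registered non-prescription product, states that intranasal use is off-label, and says that the previous tests were done in vitro only.

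Secondary outcomes measures adverse events by self-report, with no separate nasal or local category.

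**The concern.** The criteria screen for general health, immune status, infection status and one drug allergy. None screens the tissue to which the product is applied. Someone with recent nasal surgery, a septal perforation or ulcer, recurrent nosebleeds or acute sinusitis can be in good general health and meet every rule.

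What is at stake is the safety of those volunteers. On the documents' own description, the carrier is meant to carry the product past the surface layer. Damaged lining is where the extent of absorption and local irritation is hardest to predict, and no human intranasal data are described that would inform it. The plan already excludes a hazard specific to the drug (allergy to tetracycline hydrochloride), so a criterion specific to the site of application would follow the same logic.

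**Working it through.** The plan states no figure on this point, so there is nothing to reproduce. The main check is a reading of the criteria against the route and the product.

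**Step 1: does any criterion reach the nose?**

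| Criterion | Reaches non-serious nasal damage or disease? |
|---|---|
| Age; negative serology and RT-PCR | No |
| Good general health | No; the wording is limited to serious problems |
| Previous COVID-19 immunization; household case | No |
| Tetracycline allergy | No; it concerns the drug, not the site |
| Lyme disease; immunocompromised | No |
| Serious illnesses, with an open-ended ending | Only if the nasal disease is serious |

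No baseline nasal history or examination is described. Followed as written, the plan admits these volunteers.

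**Step 2: does the route make this matter?** Interventions puts the drops inside the nose for 21 days. Background and aim describes penetration beyond the mucus layer, off-label nasal use, and no human intranasal data. The application site is therefore the tissue most directly exposed, and it is the one that is not screened.

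**Step 3: how likely is it that someone affected is enrolled?** The documents give no prevalence *q*, so *q* is assumed. With independent volunteers and 50 in the active arm, P(at least one affected) = 1 − (1 − *q*)^50, and the expected number is 50*q*.

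| Assumed *q* | Expected in active arm | P(at least one) |
|---|---|---|
| 2% | 1 | 1 − 0.98^50 = 0.64 |
| 5% | 2.5 | 1 − 0.95^50 = 0.92 |
| 10% | 5 | 1 − 0.90^50 = 0.995 |

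This shows how readily the gap could be filled. It says nothing about how often harm would follow.

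**Step 4: would including them weaken the adverse-event comparison?** All rates here are assumed. With healthy lining, 5% of placebo and 20% of active volunteers report an event. With affected lining, 50% on placebo report one. At *q* = 10% each arm's rate is 0.9 × (healthy rate) + 0.1 × (affected rate). Power is that of Fisher's exact test, two-sided 0.05, 50 per arm.

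| Scenario | Placebo rate | Active rate | Power |
|---|---|---|---|
| Nobody affected | 0.05 | 0.20 | 0.51 |
| Affected: 50% vs 50% | 0.045 + 0.050 = 0.095 | 0.18 + 0.050 = 0.230 | 0.35 |
| Affected: 50% vs 65% (same 15-point difference) | 0.095 | 0.18 + 0.065 = 0.245 | 0.42 |
| Affected: 50% vs 90% | 0.095 | 0.18 + 0.090 = 0.270 | 0.54 |

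Power falls if the product adds nothing, or only the same difference, in affected volunteers. In the last row, where they react more to it, power rises slightly. The direction depends on a quantity nobody has measured.

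**The case against.** Several stronger readings are tempting, and the documents do not support them.

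- **That affected volunteers would blur the tolerability result.** Step 4 shows no fixed direction, and the safety premise (a stronger reaction to the active product) is the case in which the signal can grow. Randomization, identical bottles and a placebo given by the same route leave noise and chance imbalance, not systematic bias. Complaints added equally to both arms leave the difference in rates unchanged. The plan also defines no local tolerability outcome; it counts self-reported events overall.
- **That efficacy would be compromised.** No section says a blocked or bleeding nose defeats the product. Even with zero effect in affected volunteers and equal infection risk, the risk difference would become (1 − *q*) times its size, a relative loss of 10% at *q* = 10%.
- **That such volunteers are being exposed.** They are eligible; nothing shows that any will enrol.
- **That the product has never been used in people.** The in-vitro remark describes previous product tests, set against the need for clinical antiviral studies, and the formulation is called a registered non-prescription topical product. The supportable statement is narrower: no human intranasal data are described.

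Two further objections have some force. The open-ended ending of the serious-illness exclusion lets an investigator refuse someone with serious nasal disease, so the gap is smaller than a bare reading of the list suggests. It does not reach common, non-serious conditions and is not a reproducible rule. Also, Background and aim looks toward wide distribution to the general population, so excluding nasal disease narrows the population studied. Recording nasal status at baseline without excluding anyone would keep that breadth, but would not reduce the exposure.

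**Conclusion.** The point holds as a modest participant-safety improvement. The eligibility list is silent on the application site, and the plan as written admits volunteers with damaged or diseased nasal lining to 21 days of intranasal use of a product described as penetrating beyond the mucus layer. That conclusion rests on the text alone. Under an assumed prevalence of 2% to 10%, at least one such volunteer in the active arm is more likely than not (0.64 to 0.995); the amount of harm cannot be sized from the documents.

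Nothing here shows a stated figure to be wrong, a biased comparison, or a threat to the primary outcome.

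**What to change.** Add one exclusion under Volunteers and recruitment: current damage to or disease of the nasal lining. Recent nasal or sinus surgery, septal perforation or ulcer, recurrent nosebleeds and acute sinusitis would serve as examples, with the exact list left to the investigator. Establish it by a short history question at the baseline evaluation that the section already mentions. Intervention, schedule, sample size and analysis are unchanged.

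The cost is one line and one question. A few volunteers are turned away, and the result will not extend to people with nasal disease, which the report should state. History alone will miss undiagnosed lesions and cannot prevent conditions that arise during the 21 days.

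### As written, the eligibility list admits adults who are pregnant or breast-feeding and adults allergic to a carrier or placebo ingredient

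*Combined protocol and SAP*

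**What the plan says.** **Eligibility (Volunteers and recruitment).** The inclusion criteria ask for "over 18 years; good general health (without serious health problems"), plus negative serology and RT-PCR for COVID-19. The exclusions are earlier COVID-19 vaccination, then "allergy to tetracycline hydrochloride; diagnosis of Lyme disease; immunocompromised", then living with a diagnosed case at baseline, and finally "serious illnesses, such as cancer, kidney failure, decompensated cardiorespiratory and metabolic diseases, etc".

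**Product (Background and aim).** The technology is a "proprietary transdermal dual carrier formulation". Of it the plan says: "This formulation provides improved dermal penetration and efficacy of topical API's". Applied topically, the product "will penetrate through and into the mucus layer and deeper". The same section describes the product as FDA-registered and non-prescription, calls the intranasal use off-label, and says that previous tests were in vitro only, so that clinical studies of viral exposure and contamination are still needed.

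**Study formulations (Interventions).** The active arm receives tetracycline hydrochloride 3% in this technology. The placebo arm receives "4 drops of a formulation composed of FDA approved inactive ingredients applied inside of the nasal channels and inside of nostrils". No carrier or placebo ingredient is named. Use is daily for 21 days, twice daily for health professionals.

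**The concern.** The plan presents the carrier as a working part of the product, but the allergy exclusion covers only the active salt. A volunteer with a known allergy to something in the carrier, or in the placebo, has no criterion that applies. Pregnancy and breast-feeding are not mentioned at all, although the inclusion criteria open the trial to adults over 18 without restriction by sex or reproductive status.

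What is at stake is who is randomised. A site that follows the list literally may enrol these volunteers into 21 days of off-label intranasal use for which the plan cites no human data. Screening matters more because adverse events are collected by self-report and measured 22 days after randomization. Volunteers do send in records of each application, but the plan describes these as a check on adherence, and it describes no earlier safety assessment.

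**Working it through.** No arithmetic applies, because the point depends on no sample size, power or event rate. The check is a literal reading of the eligibility list against two volunteer profiles, both otherwise healthy.

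| Criterion | Pregnant or breast-feeding | Known allergy to a carrier or placebo ingredient, not to tetracycline hydrochloride |
|---|---|---|
| Over 18, good general health | Met | Met |
| Negative serology and RT-PCR | Can be met | Can be met |
| Excluded: earlier COVID-19 vaccination | Does not follow | Does not follow |
| Excluded: allergy to tetracycline hydrochloride | Does not apply | Does not apply (different substance) |
| Excluded: Lyme disease, immunocompromised | Does not follow | Does not follow |
| Excluded: diagnosed case in the household | Does not follow | Does not follow |
| Excluded: serious illnesses, open-ended | Not an illness | Not of the kind listed |

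**Does the open ending close the gap?** The wording is "serious illnesses, such as cancer, kidney failure, decompensated cardiorespiratory and metabolic diseases, etc". The closing abbreviation extends the examples of serious illness. It does not extend the whole list of exclusions, so it reaches neither profile on an ordinary reading.

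**Does another section close it?** Background and aim, Trial design, Ethics, Randomization and blinding, Interventions, Outcomes and Statistical analysis were read for pregnancy, breast-feeding, contraception, pregnancy testing, and hypersensitivity to carrier or placebo ingredients. None mentions any of them.

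**Who has to be suitable for what?** Eligibility is determined before concealed allocation, and the bottles look identical. Each of the 100 planned volunteers (50 per group) may receive either formulation. The exclusions therefore have to cover the ingredients of both formulations for every entrant.

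**The case against.** The strongest reply is that this is silence and not contradiction. The product is described as FDA-registered and non-prescription, an ethics committee approved the study, and written consent comes before enrolment. An investigator could use the good-health criterion to turn away a volunteer with a known relevant allergy, and the consent form, which was not available for this review, might carry a warning. It is correct that the eligibility list contradicts nothing elsewhere, and that nothing can be inferred about actual practice. But approval does not supply a missing criterion, a warning is not an exclusion, and registration does not settle who should enter a trial of a route the plan itself calls off-label.

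Several stronger readings are tempting, and the documents do not support them:

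- **That tetracycline allergy is the only product-related exclusion.** The plan gives no reasons for excluding Lyme disease, immunocompromise or kidney failure, and any of them could relate to the product. None covers the groups at issue.
- **That the product has never been used in humans.** The in vitro remark concerns the earlier tests, and the plan contrasts them with clinical studies of viral exposure and contamination. The product's registered, non-prescription status appears in the same section.
- **That reactions to a shared vehicle would blur the adverse-event comparison.** The plan does not say that the two formulations share any ingredient. Identical bottles do not imply identical vehicles.
- **That the allergy criterion is irrelevant for the placebo half of the trial.** Because eligibility precedes allocation, the 50/50 split measures nothing here.
- **That fetal or infant exposure is shown.** The statement that the product "as a topical application will penetrate through and into the mucus layer and deeper" is not a statement of systemic absorption, and the plan gives no absorption or reproductive data.

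**Conclusion.** The gap is real and narrow. Read literally, the list admits healthy adults who are pregnant or breast-feeding, and adults with a known allergy to a carrier or placebo ingredient. The pregnancy and breast-feeding part is the clearer of the two. The ingredient part is harder to judge because the plan names no ingredients.

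The number of volunteers affected cannot be derived, since the documents give no expected sex distribution, pregnancy frequency or allergy frequency, and any percentage would be a guess. The point is one of participant safety and has no shown effect on the primary outcome or its analysis. It rests on two assumptions: that sites enrol from the list as worded, and that no unavailable page of the document adds an exclusion. It is worth acting on because the change is small and determines who may be randomised.

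**What to change.** In Volunteers and recruitment:

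1. Add an exclusion: *pregnant or breast-feeding at baseline*.
2. Extend the existing allergy exclusion to *known hypersensitivity to any ingredient of either study formulation*. This keeps tetracycline hydrochloride. The documents give no basis for widening it to the whole tetracycline class.
3. Ask both at the baseline evaluation, before allocation. The person screening needs the ingredient lists of both formulations. Putting the same questions to everyone before allocation does not threaten the blinding.

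If the sponsor does intend to enrol any of these groups, the plan should say so and give the supporting data.

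The cost is one new criterion, one reworded criterion and two baseline questions, with the possible loss of a few otherwise eligible volunteers. The design, the planned 100 volunteers and the analysis stay as they are.

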## *Randomization and blinding*

Prior to initiation of the treatment, patients will be randomized into their respective intervention groups: APT™ T3X or placebo. Randomization will be generated by a website (<http://random.org/>) and performed by a participating researcher not involved in the recruitment and evaluation of the volunteers. This researcher will be instructed not to disclose the

randomization codes in the intervention groups to any of the volunteers and to the other researchers involved in the study, until its completion. The intervention bottles will be exactly the same regardless of whether it was APT™ T3X or placebo. Concealed allocation will be achieved through the use of sequentially numbered, sealed, and opaque envelopes.

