#### **Secondary outcomes**

The secondary outcomes will be presence of adverse events, number of adverse events and frequency of adverse events measured through self-report. In addition, other virus or bacteria contamination rate will be measured through the rate of how many people will be infected with influenza or pneumonia over the course of the study in each group. All secondary outcomes will be measured 22 days after the randomization i.e., after 21 days of application with APT™ T3X or placebo.

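### The randomization codes may not be disclosed to volunteers or study researchers until the study ends, and no emergency exception is written

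*Combined protocol and SAP*

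**What the plan says.** The combined protocol and SAP deals with blinding in two sections.

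- **Trial design** calls the trial "triple-blinded (volunteers, care provider, and outcome assessor", so the care provider is one of the blinded roles.
- **Randomization and blinding** says the randomization is "performed by a participating researcher not involved in the recruitment and evaluation of the volunteers". That researcher is barred from disclosing "randomization codes in the intervention groups to any of the volunteers and to the other researchers involved in the study, until its completion". On the product it adds: "The intervention bottles will be exactly the same regardless of whether it was APT™ T3X or placebo". Envelopes appear in one sentence only: "Concealed allocation will be achieved through the use of sequentially numbered, sealed, and opaque envelopes".

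Four other sections bear on the hazard.

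- **Volunteers and recruitment** lists "allergy to tetracycline hydrochloride" among the exclusion criteria.
- **Interventions** gives the active arm "4 drops of tetracycline hydrochloride 3% (APT™ T3X) applied inside of the nasal channels and inside of nostrils".
- **Background and aim** describes the intranasal use as off-label and says earlier tests of the product were in vitro only.
- **Secondary outcomes** covers safety through "presence of adverse events, number of adverse events and frequency of adverse events measured through self-report", measured 22 days after randomization.

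**The concern.** Many protocols simply leave emergency unblinding out, and a site procedure can then fill the gap. Here there is a positive instruction with an end date and no exception. If a volunteer has a serious reaction, the researcher who knows the allocation is told to withhold it both from the volunteer and from colleagues in the study.

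Two things are at stake. The first is safety: the trial's care provider and the volunteer have no sanctioned way to find out whether the volunteer received tetracycline. The second is the blinding. With no agreed route for revealing one code, a disclosure under pressure would have to be improvised, and nothing written limits it to one volunteer or keeps it from the outcome assessor.

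**Working it through.** The plan gives no figure to reproduce and the point depends on none. The check is a reading of the sections side by side.

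1. **Who knows the allocation?** Randomization and blinding names one researcher, outside recruitment and evaluation, and bars disclosure to the other study researchers.
2. **Who may not be told?** Two groups are named: volunteers and the other researchers in the study. The bar lasts until the study is complete, not until a volunteer's own 21 days of application are over. A volunteer who reacts early would wait for the whole trial to finish. The recruitment period is not stated, so the length of that wait cannot be calculated.
3. **Can the care provider be told?** If the care provider is a study researcher, the non-disclosure rule applies. If not, Trial design still keeps that role blinded. Neither section makes an exception.
4. **Can the arm be learned another way?** Not from the bottle, since the bottles are identical. The envelopes are described only as the means of concealing allocation; their holder, their retention and any emergency use are not stated.
5. **Does another section supply a route?** Reading from Background and aim through Statistical analysis, no code break, emergency unblinding or safety exception appears. Self-report of adverse events, measured at 22 days, gives no access to the allocation. Statistical analysis does not say how an unblinded volunteer would be handled.
6. **Can the hazard be set aside on the plan's own terms?** The allergy exclusion can act only on an allergy already known at entry, so a first reaction during treatment remains possible. The documents report no clinical safety data for the intranasal use.

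**Reach.** The rule applies to all 100 volunteers, 50 per group. A request could arise in either arm, because the person asking would not know which it was. One code break under a single-volunteer rule would affect the blinding of 1/100 = 1% of volunteers, or 1/50 = 2% of one arm. Disclosure of the full list would affect all 100.

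**Frequency.** This cannot be obtained from the documents. For an assumed probability p that an active-arm volunteer needs a code break, the chance of at least one among 50 is 1 − (1 − p)^50:

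| Assumed p | Chance of at least one |
|---|---|
| 0.1% | 1 − 0.999^50 = 0.049 |
| 1% | 1 − 0.99^50 = 0.395 |
| 2% | 1 − 0.98^50 = 0.636 |

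The result moves from about 5% to about 64% on the choice of p alone. The table shows why no frequency should be claimed; the conclusion does not use it.

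**The case against.** The strongest reply is that the text prohibits less than it seems to. It bars disclosure to volunteers and study researchers, not to everyone. The volunteers are instructed to use the drops every day over 21 days, and nothing says that the trial's care provider would be the one to treat a serious reaction. For a clinician outside the study, the protocol is silent rather than prohibitive. This stands, and it limits the point to the trial's own care provider and the volunteer. It does not remove the point, because an outside clinician is given no route either.

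Three stronger readings are tempting and are not supported.

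- **That one person has sole custody of the codes.** This is an inference. The protocol names one researcher but never says that no one else holds the codes, and it does not say who keeps the envelopes.
- **That the allergy exclusion contradicts the non-disclosure rule.** It does not: a site can follow both. The exclusion is an eligibility criterion and does not say that reactions are expected. It shows only that the protocol recognises tetracycline allergy as relevant.
- **That a code break is likely.** No rate in the documents supports this.

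It can also be said that a clinician already knows the product is either tetracycline 3% or inactive ingredients and may be able to treat without the code. That may be so in some cases. It does not help a volunteer who wants to know before the study ends whether tetracycline was involved. Likewise, that an improvised disclosure would reach the outcome assessor is a possibility, not a demonstrated outcome, and no effect on the primary comparison has been shown.

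Finally, emergency arrangements might sit in consent pages or site procedures not seen here, and the Ethics section commits the trial to the Declaration of Helsinki. A general commitment names no code holder and no procedure. An arrangement elsewhere that let study staff or volunteers learn a code would still have to be reconciled with the non-disclosure rule as it reads.

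**Conclusion.** The concern holds in limited form. The non-disclosure rule has an end date and no exception, the care provider is blinded, and no section provides a code break. Followed as written, it leaves the trial's care provider and the volunteer unable to learn the allocation after a serious reaction until the study is complete.

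It applies to all 100 volunteers; how many would ever need a code break is unknown. The conclusion assumes only that the sections available are the operative text on blinding. It calls neither the primary analysis nor the planned comparison into question. It is a cheap improvement to the protocol.

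**What to change.** Reconcile Trial design with Randomization and blinding by amending the non-disclosure rule so that a single volunteer's code can be disclosed, with documentation, through the researcher who already knows the allocation. What triggers a break and who receives the code are clinical decisions for the sponsor and investigator to define; no wording for them is proposed here.

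The amendment should also state that:

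- each break is logged with its date and reason;
- the outcome assessor stays blinded;
- the volunteer remains in the analysis in the assigned arm.

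The protocol does not describe how bottles are labelled. Before relying on single-code disclosure, confirm that one volunteer's code does not reveal anyone else's.

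The cost is one or two sentences and a log sheet, with no new role, since the researcher outside recruitment and evaluation already exists. The downside is lost blinding for the few volunteers concerned.
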